8.1.1.3. Imaging

CT or MRI or urogram of the abdomen and pelvis/urinary tract are the recommended imaging modalities. Other areas may be scanned as clinically indicated. Imaging should be performed with contrast agents unless contraindicated for medical reasons. The same imaging technique used at screening will be employed in the tumor assessments conducted on study.

For Cohort B1, disease status will be assessed through imaging at screening, every 24 weeks for 2 years after initiation of study intervention. Imaging will be performed until persistence of CIS, recurrence of high-grade disease or disease progression, consent withdrawal, lost to follow-up, EOT, or death. Additional imaging may be performed as clinically indicated. For Cohort A and Cohort B2, imaging is done as clinically indicated.

Guidance for integration of imaging in the disease assessment are provided in the disease assessment decision algorithm in Section [10.9](#).

Independent reviewers will provide central assessment prior to registration for Cohort B1, and retrospective central assessment of all imaging for Cohorts A and B1. Refer to the manual for process details on sending the scans for the BICR assessment.

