### 3. ENDPOINTS AND BASELINE VARIABLES: DEFINITIONS AND CONVENTIONS

#### 3.1. Primary Endpoint

##### Cohort A

- EFS for Arm A vs Arm C as assessed by the investigator

EFS is defined as time from randomization to the earliest of recurrence of high-grade disease, progression of disease, persistence of CIS, or death due to any cause.

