**Recurrence of low-grade disease** is defined as re-appearance of low-grade disease (low-grade Ta) after ‘start date’. This will require a cystoscopy or cytology positive result, with biopsy positive for low-grade Ta. The date of positive biopsy, cystoscopy, or cytology (whichever positive result is earliest) will be used as the date of recurrence of low-grade disease.

**Progression of disease is defined** as any of the following:

- Lamina propria invasion (e.g., increase from Ta to T1 or CIS to T1)
- Muscle invasive disease (stage  $\geq$  T2)
- Lymph node positive disease (N+)
- Metastatic disease (M1)
- Appearance of high-grade Ta or T1 in participants with CIS only at baseline (Cohort A and Cohort B1) before achieving a CR.

This will require a cystoscopy or cytology positive result with imaging positive and/or biopsy positive for disease progression as described above. The date of positive biopsy, imaging for new lesion, positive cystoscopy, or positive cytology (whichever result is earliest) will be used as the date of progression.

**No Evidence of Disease:** only applies to participants without CIS at baseline (Cohort A and Cohort B2) and is defined as disease that was completely resected prior to ‘start date’ and does not meet the criteria of progression of disease, recurrence of high-grade disease, or recurrence of low-grade disease while on study.

The date of imaging, biopsy, cystoscopy, or cytology (whichever result of the available assessments is earliest) that supports no evidence of disease will be used as the date of no evidence of disease.

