### 6.1. Primary Endpoint(s)

#### 6.1.1. Event-free survival as assessed by investigator (Cohort A only)

##### 6.1.1.1. Primary analysis (for Arm A vs Arm C)

Refer to [Section 2.2.1](#) for the primary estimand.

In this study, disease may be assessed through cytology, cystoscopy, biopsy, and imaging scans conducted at screening (required), every 12 weeks for 2 years following randomization, and every 24 weeks thereafter until first occurrence of progression of disease, recurrence of high-grade disease, or persistence of CIS (for participants with CIS at baseline) regardless of initiation of subsequent anti-cancer therapy.

EFS is defined as the time from randomization until progression of disease, recurrence of high-grade disease, persistence of CIS, or death due to any cause, whichever occurs first.

An event is as defined in Table 10. The censoring and event date options to be considered for the EFS analysis ([Section 2.2.1](#)) are presented in Table 11.

$$\text{EFS (months)} = [\text{date of event or censoring} - \text{date of randomization} + 1]/30.4375$$

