**Table 11. Outcome and Event Dates for the Primary Analysis of EFS-Cohort A**

Scenario	Date of event/censoring	Outcome
No adequate baseline assessment	Date of randomization [a]	Censored [a]
Event - After at most one missing or inadequate post-baseline disease assessment, OR - $\leq 24$ weeks after the date of randomization	Date of event	Event
Event - After 2 or more missing or inadequate post-baseline disease assessments	Date of last adequate disease assessment documenting no event	Censored
No event	Date of last adequate disease assessment documenting no event	Censored

[a] However, if the participant dies  $\leq 24$  weeks after the date of randomization the death is an event with date on death date

The primary efficacy analysis will compare the EFS time based on the investigator assessment between Arm A and Arm C and will be performed using a 1-sided stratified log-rank test as described in [Section 5.1](#). The following analyses will be based on the FAS.

The treatment effect will be estimated using a Cox's Proportional Hazard model stratified by the randomization strata to calculate the hazard ratio along with 95% CIs. Each stratum will define a separate baseline hazard function (using the 'STRATA' statement in SAS PROC PHREG), ie for the i-th stratum the hazard function is expressed as:  $h(i;t) = h(i,0;t) \exp(x\beta)$ ,

where  $h(i,0;t)$  defines the baseline hazard function for the  $i$ -th stratum and  $x$  defines the treatment arm (0=control arm, 1= experimental arm) and  $\beta$  is the unknown regression parameter.

Ties will be handled using the Exact option in SAS (Ties=Exact option in SAS PROC PHREG).

Kaplan-Meier estimates (product-limit estimates) will be presented by treatment arm together with a summary of associated statistics including the median EFS time with 2-sided 95% CIs. In particular, the EFS rate at 6, 12, 18, 24, 30, 36, 42, and 48 months will be estimated with corresponding 2-sided 95% CIs. The CIs for the median will be calculated according to Brookmeyer and Crowley (1982) and the CIs for the survival function estimates at the time points defined above will be derived using the log-log transformation according to Kalbfleisch and Prentice (2002) (conftype=loglog default option in SAS Proc LIFETEST) with back transformation to a CI on the untransformed scale. The estimate of the standard error will be computed using Greenwood's formula. A Kaplan-Meier plot for EFS will be generated.

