**Table 12. EFS Censoring Reasons and Hierarchy – Cohort A**

Hierarchy	Condition	Censoring Reason
1	No adequate baseline assessment	No adequate baseline assessment[a]
2	Event after 2 or more missing or inadequate post-baseline disease assessments	Event after 2 or more missing assessments
3	No event and [withdrawal of consent date $\geq$ date of randomization]	Withdrawal of consent
4	No event and lost to follow-up in any disposition page	Lost-to-follow-up
5	No event and [EOS][b] present OR all EOT disposition pages of all drugs in the treatment arm say participant will not continue into any subsequent phase of the study] and no adequate post-baseline disease assessment	No adequate post-baseline disease assessment
6	No event and none of the conditions in the prior hierarchy are met	Ongoing without an event

[a] However, if the participant dies  $\leq$ 24 weeks after the date of randomization the death is an event with date on death date

[b] EOS here refers to completion of follow-up disposition page.

For the participants with a PD event for EFS as assessed by the investigator, the number and percentage of participants with the following types of PD (defined hierarchically) will be presented:

- Progression to metastatic disease (defined as N+, M+)
- Progression to muscle invasive disease (defined as  $\geq$  T2 disease)
- Stage Progression (defined as high-grade Ta or T1 disease)

The EFS time or censoring time and the reasons for censoring will also be presented in a participant listing.

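### The written progression rule requires a positive cystoscopy or cytology even for nodal and metastatic disease, so spread with negative or missing bladder findings is not an EFS progression event when it is shown

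*SAP*

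**What the plan says.** EFS by investigator is the primary endpoint (Arm A vs C) and the first key secondary endpoint (Arm B vs C). SAP 3.1 ends EFS at the earliest of "recurrence of high-grade disease, progression of disease, persistence of CIS, or death due to any cause".

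SAP 5.2.12 lists five forms of progression: lamina propria invasion, muscle invasion, N+, M1, and new high-grade Ta or T1 before CR in participants with CIS only. A single evidence rule follows the list: "This will require a cystoscopy or cytology positive result with imaging positive and/or biopsy positive for disease progression as described above". Protocol 10.9 (Appendix 9) carries the same list and the same sentence. SAP 5.2.12 presents its definitions as the rules by which disease will be assessed.

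Related provisions:

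- **Imaging** (protocol 8.1.1.3): "For Cohort A and Cohort B2, imaging is done as clinically indicated". The Schedule of Activities gives its purpose as checking for distant metastasis.
- **Schedule** (SAP 6.1.1.1): disease assessment is "every 12 weeks for 2 years following randomization, and every 24 weeks thereafter until first occurrence of progression of disease" or another disease event.
- **No evidence of disease** (SAP 5.2.12, participants without CIS at baseline): disease resected before the start date that meets none of the progression or recurrence criteria. It is dated by "The date of imaging, biopsy, cystoscopy, or cytology (whichever result of the available assessments is earliest) that supports no evidence of disease".
- **Censoring** (SAP Table 11): an event "After 2 or more missing or inadequate post-baseline disease assessments" is censored at the last adequate assessment showing no event, unless it falls within 24 weeks of randomization.
- **Planned output** (SAP 6.1.1.1, after Table 12): progression events are to be broken down by type. The first type is progression to metastatic disease, defined as N+ or M+.

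**The concern.** Cystoscopy and urine cytology examine the bladder and urine. They do not examine lymph nodes or distant organs. A positive bladder or urine result is a sensible requirement for intravesical disease, but for N+ and M1 it makes recognition of spread depend on a test that does not look for it.

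If the rule is applied as written, the gravest non-death component of the primary endpoint can go uncounted, or be dated only at a later bladder finding or at death. If some sites instead record such cases as progression on clinical judgement, coding departs from the text and may differ between sites. The experimental arms add a systemic agent to local BCG, so the arms could differ in extravesical spread. That last point is a reason for care; the documents contain no figure to support it.

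**Working it through.** **1. The rule applied to four cases**

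- *Clear bladder, negative cytology, imaging or biopsy shows N+ or M1.* The imaging or biopsy half is met; the cystoscopy or cytology half is not. The case is not progression. If the participant had no CIS at baseline and no high- or low-grade recurrence, the wording for no evidence of disease fits. SAP 5.2.11 accepts that result as an adequate assessment, so under Table 11 the visit documents no event.
- *The same, with positive cytology.* The rule is met. Protocol 8.1.1.2 counts cytology suspicious for high-grade carcinoma as positive. A later positive bladder finding would also meet it.
- *Spread after a cystectomy done for high-grade recurrence, progression or persistent CIS.* The EFS event has already occurred, so the rule has no effect.
- *Spread after a cystectomy without a prior EFS event.* Cystoscopy is no longer possible (an inference), so only positive cytology could satisfy the rule. Neither document gives a post-cystectomy assessment rule, and cystectomy is neither an event (Table 10) nor a primary censoring reason (Table 12).

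**2. Whether another planned analysis recovers the spread (SAP 6.2.2.3)**

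- EFS by BICR uses the same event table (Table 10), and no separate progression definition is given.
- The BICR confirmation summary starts from non-death events that the investigator already called, so it cannot reveal uncalled ones.
- The analysis that drops missed-assessment censoring recovers a later death but not the earlier spread.

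**3. The later death**

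Under Table 11 the death counts if at most one assessment was missing or inadequate before it, or if it fell within 24 weeks of randomization. Otherwise it is censored.

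To show how much this could matter, assume that assessments stop at spread and that survival afterwards is exponential with median m months. Neither assumption is in the documents. The second missed visit then falls 12–24 weeks after spread on the 12-week schedule, or 24–48 weeks on the 24-week schedule. The share of deaths after w weeks is exp(−ln 2 × (7w/30.4375)/m):

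| m (months) | 12-week schedule | 24-week schedule |
|---|---|---|
| 6 | 53–73% | 28–53% |
| 12 | 73–85% | 53–73% |
| 24 | 85–92% | 73–85% |

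If assessments continue and are recorded as adequate, the share is zero.

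**4. Power**

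Inputs from SAP 5.1.1: HR 0.69, 174 events, 1-sided alpha 0.025, equal allocation. Power = Φ(√(174/4) × |ln 0.69| − 1.96) = Φ(6.596 × 0.3711 − 1.96) = Φ(0.487) = 68.7%, which matches the plan. For Arm B vs C at alpha 0.023 the same formula gives 67.4%, which also matches.

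The 174 is projected from blinded observed EFS accrual (protocol 9.2.1, SAP 5.1.1). Any events that the rule excludes are already absent from it, so subtracting them again would double-count. If the correction added 2, 5, 10 or 15 events to a two-arm comparison (assumed counts, with the same HR), power would be 69.2%, 69.9%, 71.1% or 72.3%. Cases that already count later at death would change date but not add to the total.

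**The case against.** The strongest counter-argument is that the controlling figure has not been seen. Protocol 8.1.1 and 8.1.1.3 send the reader to the Appendix 9 decision algorithm for integrating imaging, and that diagram is not in the available text. An imaging-only path may be there. If so, the defect is a contradiction between figure and text, which still has to be reconciled.

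The plan also clearly intends N+ and M1 to count. They are listed, imaging for a new lesion is a permitted progression date, and a table is planned for them. Investigators may therefore have recorded such cases as progression, and no visible text says that a program would override them. This lowers the likely number affected. It does not remove the conflict, because the written rules say otherwise.

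A looser parse, in which a positive biopsy stands alone, would admit biopsy-proven spread. The parallel sentences for recurrence and persistence pair a positive cystoscopy or cytology with biopsy, so the conjunctive reading is the natural one.

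On deaths, the objection largely stands. With no EFS event recorded, protocol 4.1.1 keeps disease assessments going, so assessments need not stop. OS and DSS do not use the Table 11 missed-assessment censoring.

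Finally, the rule is the same in every arm, and changing a primary event definition late in an open-label trial carries its own risk. Both points are fair. The second bears on how the correction is made.

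**Conclusion.** The written definition is internally inconsistent and should be corrected. N+ or M1 shown by imaging or biopsy, with cystoscopy and cytology negative or not done, is not an EFS progression event at that date. This includes spread after a cystectomy without a prior EFS event. A participant without CIS at baseline could then be classed as disease-free.

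The size is unknown: the documents give no count or rate of such cases. The conclusion rests on the text of SAP 5.2.12 and protocol 10.9 being applied literally, and on the unseen diagram not overriding it.

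A reader might infer four stronger things that the documents do not support:

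- *Such spread is never an event.* Positive cytology, or a later positive bladder finding, satisfies the rule.
- *Every cystectomy hides later progression.* Only a cystectomy without a prior EFS event matters.
- *The subsequent death is lost.* It is lost from the primary analysis only under the two Table 11 conditions together, and a planned sensitivity analysis restores it.
- *Power falls below 68.7%, or the hazard ratio is biased a known way.* The event projection already reflects recorded accrual, and nothing indicates a direction of bias.

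The issue is which events the primary endpoint counts and when they are dated; power is secondary.

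**What to change.** For the EFS analysis, in SAP 5.2.12 and protocol 10.9:

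- Limit the positive cystoscopy or cytology condition to intravesical progression.
- State that N+ or M1 shown by imaging or biopsy is progression whatever the bladder findings, dated at that imaging or biopsy. Say explicitly that this holds after cystectomy.
- Reconcile both texts with the Appendix 9 diagram.

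Before database release, query existing imaging, biopsy, subsequent-therapy and death records for participants coded event-free, without reference to treatment arm.

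The cost is wording in two documents, one programming rule and a data query, with no new procedure. The downside is that a few events need re-adjudication in an open-label trial, so the query rule should be fixed in writing before by-arm summaries are available. SAP section 2 says that major changes to the primary endpoint definition are also reflected in a protocol amendment, so this change should appear in one.

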### 5.3. Methods to Manage Missing Data

#### 5.3.1. Missing data

Unless otherwise specified, all data will be evaluated as observed, and no imputation method for missing values will be used.

In all participant data listings imputed values will be presented and flagged as imputed.

Missing statistics, e.g. when they cannot be calculated, should be presented as ‘ND’ for not done, ‘NR’ for not reached or ‘NA’ for not applicable. For example, if N=1, the measure of variability cannot be computed and should be presented as ‘ND’ or ‘NA’.

### **5.3.1.1. Pharmacokinetic concentrations**

#### **Concentrations Below the Limit of Quantification**

All concentrations assayed as below the level of quantification (BLQ) will be set to zero. The BLQ values will be excluded from calculations of geometric means and their CIs. A statement similar to ‘All values reported as BLQ have been replaced with zero’ should be included as a footnote to the appropriate tables and figures.

In listings, BLQ values will be reported as “<LLQ”, where LLQ will be replaced with the value for the lower limit of quantification.

#### **Deviations, Missing Concentrations and Anomalous Values**

In summary tables and plots of median profiles, concentrations will be set to missing if one of the following cases is true:

- 1) A concentration has been reported as ND (i.e., not done) or NS (i.e., no sample);
- 2) A deviation in sampling time is of sufficient concern or a concentration has been flagged as anomalous by the clinical pharmacologist.

Summary statistics will not be presented at a particular time point if more than 50% of the data are missing. No values will be imputed for missing data.

### **5.3.2. Handling of incomplete dates**

#### **5.3.2.1. Adverse events**

Incomplete AE-related dates will be imputed as follows:

- If the AE onset date is missing completely, then the onset date will be replaced by the start of study treatment.
- If only the day part of the AE onset date is missing, but the month and year are equal to the start of study treatment, then the AE onset date will be replaced by the start of study treatment. For example, if the AE onset date is --/JAN/2015, and study treatment start date is 15/JAN/2015, then the imputed AE onset date will be 15/JAN/2015.
- If both the day and month of the AE onset date are missing but the onset year is equal to the start of study treatment, then the onset date will be replaced by the start of study treatment. For example, if AE onset date is --/---/2014, and study treatment start date is 19/NOV/2014, then the imputed AE onset date will be 19/NOV/2014.
- In all other cases the missing onset day or missing onset month will be replaced by 1.
- Incomplete stop date will be replaced by the last day of the month (if day is missing only), if not resulting in a date later than the date of participant’s death. In the latter case the date of death will be used to impute the incomplete stop date.
- In all other cases the incomplete stop date will not be imputed. If stop date of AE is after the date of cut-off outcome of AE is ongoing at cut-off.

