8.3.1. Time Period and Frequency for Collecting AE and SAE Information

The time period for actively eliciting and collecting AEs and SAEs (“active collection period”) for each participant begins from the time the participant provides informed consent, which is obtained before the participant’s participation in the study (ie, before undergoing any study-related procedure and/or receiving study intervention), through and including a minimum of 90 calendar days after the last administration of the study intervention.

For participants who are screen failures, the active collection period ends when screen failure status is determined.

Follow-up by the investigator continues throughout and after the active collection period and until the AE or SAE or its sequelae resolve or stabilize at a level acceptable to the investigator and Pfizer concurs with that assessment.

For participants who are screen failures, the active collection period ends when screen failure status is determined.

If the participant withdraws from the study and also withdraws consent for the collection of future information, the active collection period ends when consent is withdrawn.

If a participant definitively discontinues or temporarily discontinues study intervention because of an AE or SAE, the AE or SAE must be recorded on the eCRF and the SAE reported using the CT SAE Report Form.

Investigators are not obligated to actively seek AEs or SAEs after the participant has concluded study participation. However, if the investigator learns of any SAE, including a death, at any time after a participant has completed the study, and he/she considers the event to be reasonably related to the study intervention, the investigator must promptly report the SAE to Pfizer using the CT SAE Report Form.

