8.3.1.2. Recording Nonserious AEs and SAEs on the eCRF

All nonserious AEs and SAEs occurring in a participant during the active collection period, which begins after obtaining informed consent as described in Section 8.3.1, will be recorded on the AE section of the eCRF.

The investigator is to record on the eCRF all directly observed and all spontaneously reported AEs and SAEs reported by the participant.

If a participant begins a new anticancer therapy, the recording period for nonserious AEs ends at the time the new treatment is started; however, SAEs must continue to be recorded on the eCRF during the above-indicated active collection period. Note that a switch to a commercially available version of the study intervention is considered as a new anticancer therapy for the purposes of SAE reporting.

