**3.5. Safety Endpoints**

**3.5.1. Adverse events**

**Treatment-Emergent Adverse Events**

Treatment-emergent adverse events (TEAEs) are those events with onset dates occurring during the on-treatment period.

**On-treatment period** is defined as the time from the first dose of study treatment through minimum (30 days + last dose of study treatment, start day of new anti-cancer drug therapy – 1 day) (also refer to Appendix 1 for irAEs). The start day of new anti-cancer drug therapy after the first dose of study treatment is derived as outlined in [Section 5.2.5](#).

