### **5.2.5. Definition of start of new anti-cancer drug therapy**

Start date of new anti-cancer drug therapy is used to determine the end of the on-treatment period (see [Section 5.2.7](#)).

The start date of new anti-cancer drug therapy is the earliest start date of anti-cancer drug therapy recorded in the ‘Follow-up Cancer Therapy’ eCRF pages that is after the first dose of study treatment. When start date of anti-cancer drug therapy is missing or partially missing, the imputation rules described in [Section 5.3.3.4](#) should be applied using only data from the ‘Follow-up Cancer Therapy’ eCRF pages.

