### 5.3.3.4. Date of start of new anti-cancer therapy

Incomplete dates for start date of new anti-cancer therapy will be imputed as follows and may be used for determining censoring dates for efficacy analyses. Event date below refers to progression of disease, recurrence of high-grade disease or persistence of CIS date by investigator assessment. If the imputation results in an end date prior to the imputed start date, then the imputed start date should be set to the end date.

- The end date of new anti-cancer therapy will be included in the imputations for start date of new anti-cancer therapy. If the end date of new anti-cancer therapy is
  - completely missing then it will be ignored in the imputations below

- partially missing with only year (YYYY) available then the imputations below will consider 31DECYYYY as the end date of the new anti-cancer therapy
- partially missing with only month and year available then the imputations below will consider the last day of the month for MMMYYYY as the end date of the new anti-cancer therapy

- For participants who have not discontinued study treatment at the analysis cut-off date, last dose of study treatment is set to the analysis cut-off date in the imputations below.
- If the start date of new anti-cancer therapy is completely or partially missing, then the imputed start date of new anti-cancer therapy is derived as follows:
  - Start date of new anti-cancer therapy is completely missing
    - Imputed start date = min [max(Event date + 1, last dose of study treatment + 1), end date of new anti-cancer therapy]
  - Only year (YYYY) for start of anti-cancer therapy is available
    - IF YYYY < Year of min [max(Event date + 1, last dose of study treatment + 1), end date of new anti-cancer therapy] THEN imputed start date = 31DECYYYY;
    - ELSE IF YYYY = Year of min [max(Event date + 1, last dose of study treatment + 1), end date of new anti-cancer therapy]
    - THEN imputed start date = min [max(Event date + 1, last dose of study treatment + 1), end date of new anti-cancer therapy]
    - ELSE IF YYYY > Year of min [max(Event date + 1, last dose of study treatment + 1), end date of new anti-cancer therapy]
    - THEN imputed start date = 01JANYYYY
  - Both Year (YYYY) and Month (MMM) for start of anti-cancer therapy are available
    - IF
      - YYYY = Year of min [max(Event date + 1, last dose of study treatment + 1), end date of new anti-cancer therapy], AND

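### SAP 5.3.2.1 makes some adverse events that ended before first dose treatment-emergent, because it imputes the onset without looking at the stop date

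*SAP*

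**What the plan says.** **Onset of adverse events.** Protocol 8.3.1 states that active collection "for each participant begins from the time the participant provides informed consent". The Cohort A schedule of activities allows a 28-day screening period and permits consent before that. SAP 3.5.1 defines treatment emergence by onset only: "Treatment-emergent adverse events (TEAEs) are those events with onset dates occurring during the on-treatment period". For incomplete onsets, SAP 5.3.2.1 states: "If the AE onset date is missing completely, then the onset date will be replaced by the start of study treatment". It treats a day-missing onset in the month and year of first dose in the same way (its example: "study treatment start date is 15/JAN/2015, then the imputed AE onset date will be 15/JAN/2015"), and likewise a year-only onset in the year of first dose ("study treatment start date is 19/NOV/2014, then the imputed AE onset date will be 19/NOV/2014"). A stop date with only the day missing becomes the last day of its month. No bullet compares the stop date with the imputed onset.

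**End of the safety window.** SAP 5.2.7 ends the on-treatment period at the earlier of 30 days after last dose and the day before new anti-cancer drug therapy starts. For incomplete start dates, SAP 5.2.5 says: "When start date of anti-cancer drug therapy is missing or partially missing, the imputation rules described in" 5.3.3.4 should be applied. For a completely missing start, that section gives: "Imputed start date = min [max(Event date + 1, last dose of study treatment + 1), end date of new anti-cancer therapy". A partial date that matches the year, or the year and month, of this reference date is set to the same value. Under SAP 5.2.7, safety data outside the window are listed with a flag but not summarized.

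**The concern.** Assigning an event to treatment is a sensible default when its timing is unknown. It is not sensible when the record itself shows that the event was over before the first dose. The onset rule then creates a record that begins after it ends and places it in the TEAE tables, although treatment cannot have caused it. It can also carry an event past step 2 of the immune-related AE definition (SAP Appendix 1), which requires onset on or after first dose.

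The second rule errs in the other direction. SAP 5.3.3.4 describes its imputed dates as possible inputs to efficacy censoring. Used to close the safety window, it can drop events in the 30 days after last dose from the TEAE, serious-event and on-treatment laboratory summaries. For safety, that is the less cautious direction.

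**Working it through.** **Inputs.** The rules come from SAP 5.3.2.1, 5.3.3.4, 3.5.1 and 5.2.7. All test dates are assumptions, apart from the SAP's own two examples.

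**Check against the SAP's examples.** Onset --/JAN/2015 with first dose 15/JAN/2015 gives 15/JAN/2015. Onset --/---/2014 with first dose 19/NOV/2014 gives 19/NOV/2014. Both match the SAP.

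**Onset rule.** Duration = stop − onset + 1 day. An event is a TEAE if its onset is on or after first dose and inside the window.

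| First dose | Recorded onset | Stop | Imputed onset | Duration (days) | TEAE |
|---|---|---|---|---|---|
| 15 Jan 2015 | missing | 10 Jan 2015 | 15 Jan 2015 | −4 | yes |
| 15 Jan 2015 | --/JAN/2015 | 10 Jan 2015 | 15 Jan 2015 | −4 | yes |
| 15 Jan 2015 | --/---/2015 | 10 Jan 2015 | 15 Jan 2015 | −4 | yes |
| 15 Jan 2015 | missing | --/DEC/2014, imputed 31 Dec 2014 | 15 Jan 2015 | −14 | yes |
| 25 Jan 2021 | --/JAN/2021 | 10 Jan 2021 | 25 Jan 2021 | 10 − 25 + 1 = −14 | yes |

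In the fourth row, the SAP's own stop-date imputation puts the end before first dose, yet the onset still moves to first dose.

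**Window rule.** Take last dose as 5 Jun 2023, with no therapy end date recorded. Reference date = max(event + 1, last dose + 1). Window end = min(5 Jul 2023, imputed start − 1).

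| Recorded start of new drug therapy | EFS event (non-death) | Imputed start | Window ends | Post-dose days kept |
|---|---|---|---|---|
| missing | none | 6 Jun 2023 | 5 Jun 2023 | 0 |
| missing | 20 May 2023 | 6 Jun 2023 | 5 Jun 2023 | 0 |
| 2023 | none | 6 Jun 2023 | 5 Jun 2023 | 0 |
| Jun 2023 | none | 6 Jun 2023 | 5 Jun 2023 | 0 |
| missing | 15 Jun 2023 | 16 Jun 2023 | 15 Jun 2023 | 10 |
| Jul 2023 | none | 1 Jul 2023 | 30 Jun 2023 | 25 |
| missing | 15 Jul 2023 | 16 Jul 2023 | 5 Jul 2023 | 30 |

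The whole window is lost only when the start is missing, or matches the year or month of last dose + 1, and no EFS event follows the last dose. For the year-only entry, 209 calendar dates remain in 2023 after 5 Jun. Of these, 209 − 30 = 179 lie more than 30 days after last dose, where a known start would have left the full window. These are counts of dates, not probabilities.

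Protocol 8.3.1.2 adds that once new anticancer therapy begins, "the recording period for nonserious AEs ends at the time the new treatment is started". A nonserious event recorded after the imputed start is therefore some evidence that the imputed date is too early, if sites follow the protocol. Serious events continue to be recorded.

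**The case against.** **Onset rule.** Resolving doubt towards treatment is the cautious convention. The analysis uses cleaned data, and an event with a known pre-dose stop is an obvious candidate for a query. Events before randomization should also be balanced across arms apart from chance. All of this stands and limits the impact. It does not justify the rule where the stop date has already removed the doubt.

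A reader might infer that the SAP has no check on negative durations at all. That goes too far. SAP 5.3.4 recognizes that resolution cannot precede onset and makes the two dates equal. But that section is headed as covering other dates, adverse events have their own rules, and it does not say which date moves. If the stop date moves, an observed date is overwritten and the event remains treatment-emergent.

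**Window rule.** A reader might infer that every incomplete therapy date erases the window, or that safety data vanish from the report. The documents support neither. An EFS event after last dose preserves some or all of the window, as shown above. Immune-related events use a 90-day window that ignores new therapy (SAP Appendix 1). Deaths within 30 days of last dose are tabulated separately (SAP 6.6.2). Out-of-window events remain in flagged listings. Using one imputation for both safety and efficacy is also at least consistent, and a later imputed date could count events that arose under another anti-cancer drug. The window point is therefore partly a choice between two errors.

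**Conclusion.** The onset rule gives a wrong result in a definable case: an onset that is missing, or partial in the month or year of first dose, with a stop date before first dose. Each such record adds one event to the TEAE tables that treatment cannot have caused. This is a minor defect that should be corrected.

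The window rule is a secondary point. In the stated configuration it keeps 0 of 30 post-dose days. Whether to replace it is a judgement for the sponsor.

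No number of affected participants can be given, because the documents report no counts of incomplete onset or therapy dates. It would be tempting to take the roughly 261 expected EFS events as the number starting new drug therapy and apply a missingness rate. That is a different quantity: it includes deaths and participants whose next treatment is surgery or radiation, whereas SAP 5.2.5 uses drug therapy only. The overall effect is probably small, and neither rule as applied to safety alters a primary or key secondary analysis.

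**What to change.** 1. Add to SAP 5.3.2.1: if the recorded or imputed stop date is before first dose, the onset is imputed no later than the stop date and the event is not treatment-emergent. In the four 2015 test cases and the 2021 example this removes the false TEAE. Uncertain cases stay as they are: a stop of --/JAN/2021 is imputed to 31 Jan 2021, after a first dose on 25 Jan 2021, so that event remains a TEAE. There is no statistical cost.

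2. Consider a separate rule in SAP 5.2.5 for the safety window only, such as the latest start date compatible with the recorded parts and any recorded therapy end date. With last dose on 5 Jun 2023, a start of 2023 would be taken as 31 Dec 2023 and keep 30 days. A start of Jun 2023 would be taken as 30 Jun 2023 and keep 24 days (window end 29 Jun). The cost is that a few events after an undated new therapy may be counted as treatment-emergent. SAP 5.3.3.4 stays unchanged for the EFS sensitivity analysis that censors at new therapy.

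Together these need about two sentences in the SAP and a small programming change.
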